9.0 Research Methods

9.1 Study Design

This study is designed as a prospective, observational study to assess the effect of adalimumab on health-related QoL and work productivity in patients with RA in China in clinical practice.

The study population will include Chinese adult patients with a diagnosis of RA who meet the requirements per the local label for treatment with adalimumab at the baseline visit. The decision to prescribe adalimumab for RA should be based on clinical practice criteria without taking participation in this study into account. Patients will be included in the study after a physician's decision of initiating Humira.

Approximately 52 patients diagnosed with RA that meet the inclusion and exclusion criteria will be enrolled at approximately 16 sites.

This study is non-interventional and the subjects/investigator will follow the current clinical practice in each site. Not additional task will be required other than current practice to keep the data as "real world data collect".

The observation period for each patient is 24 weeks. All visits are to be scheduled as per routine clinical practice, regardless of study participation. Patients may discontinue adalimumab treatment or the study at any time without prejudice.

The physician will follow the patient during regular clinic visits at intervals as determined by routine clinical practice. Data at the clinic visits within ± 7 days of the study-defined time points will be collected and data at the clinic visits closest to the study-defined time points will be used for statistical analysis (If there are 2 clinic visits equidistant from a study-defined time point which do not correspond to any other visit, data from the EARLIER clinic visit shall be used for the study-defined time point).

The HAQ DI data will be collected at baseline, Week 12 and Week 24 after treatment initiation with adalimumab, as per standard daily clinical practice. In addition, when available, other PROs of work activity and well-being, including the WPAI, EQ-5D, and SF-36, will also be collected.

The HCRU will also be collected, when available. This includes surgical procedures, hospitalizations, bed days in hospital, physician consultations etc. Costs will be assigned based on the HCRU using standardized costs for each participating countries.

Primary Endpoint

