9.1.1 Study Activities

Table 1 Study Activities (Day 1/Baseline Through 6 months)

	Data Collection/Observation	Baseline ^a	Week 12 (V2) ± 7 days	Week 24 (V3) ± 7 days	Early Termination / Drop out	70 days after the Week 24 or the last dose	150 days after the Week 24 or the last dose
Clinician Packet	Inclusion/exclusion form	X					
	Clinical history/patient demographics	X					
	Comorbidities	X					
	DAS28 (ESR) or DAS28 (CRP)	X	X	X	X		
Patient Packet	EuroQoL 5-Dimension (EQ-5D)	X	X	X	X		
	Short Form 36-Item Health Survey (SF-36)	X	X	X	X		
	Health Assessment Questionnaire (HAQ)	X	X	X	X		
	Work Productivity and Activity Impairment Questionnaire (WPAI)	X	X	X	X		
	Healthcare Resource Utilization (HCRU)	X	X	X	X		
	Patient Global Impression of Change (PGIC)		X	X	X		
	Patient Treatment Satisfaction Questions	X	X	X	X		
Clinical n	Adverse events (including malignancy)	←				→	
	Pregnancy	←					→

a. The Baseline visit date will serve as the reference for all subsequent visits. A \pm 7 day window is permitted around scheduled study visits.

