9.2.4.7 Study Documents

Clinical case report form (CRF)

The clinical CRF will document the patient's current status (moderate, severe RA), Disease Activity Score in 28 joints (DAS28), prior and current treatments and other relevant clinical and demographic data to be used in segmenting the population during analysis.

To calculate the DAS28 the physician or specialist nurse will:

1. Count the number of swollen joints (out of the 28)
2. Count the number of tender joints (out of the 28)
3. Take blood to measure the erythrocyte sedimentation rate (ESR) or C reactive protein (CRP); the latest measurement in the medical records may also be used if a blood draw is not standard for that visit
4. Ask the patient to make a 'global assessment of health' which will be indicated by marking a 10 cm line between very good and very bad

The physician or specialist nurse will then mark each component score on the CRF and the DAS28 score if calculated (an online scoring calculator for the DAS28 can be found at <http://www.das-score.nl/das28/DAScalculators/dasculators.html>).

The DAS28 will be scored using the following formula:

$$\text{DAS28(CRP)} = 0.56 * \text{sqrt}(\text{tender28}) + 0.28 * \text{sqrt}(\text{swollen28}) + 0.36 * \ln(\text{CRP}+1) + 0.014 * (\text{Patient Global assessment of Health in mm})+0.96$$

$$\text{DAS28(ESR)} = 0.56 * \text{sqrt}(\text{tender28}) + 0.28 * \text{sqrt}(\text{swollen28}) + 0.70 * \ln(\text{ESR}) + 0.014 * (\text{Patient Global assessment of Health in -mm})$$

DAS28 scores will be interpreted using the following categorization:

- Remission: $\text{DAS28} \leq 2.6$
- Low Disease activity: $2.6 < \text{DAS28} \leq 3.2$
- Moderate Disease Activity: $3.2 < \text{DAS28} \leq 5.1$
- High Disease Activity: $\text{DAS28} > 5.1$

The full CRF is presented in **Error! Reference source not found.**

PRO questionnaires

The following PRO questionnaires will be included in the patient questionnaire packet.

Health Assessment Questionnaire Disability Index (HAQ DI)

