9.7.6 Additional Secondary Endpoint Analysis

Additional efficacy analysis include:

- Change in HAQ DI score at 24 weeks after the initiation of adalimumab, in those patients continuing on adalimumab, compared with those patients not continuing on adalimumab. The mean changes in these two groups will be compared using an independent t-test.
- Healthcare resource utilization will be described using number and percentage within each category (number of consultations, number of procedures received, number of surgeries, number of hospitalizations and length of stay, number of concomitant medications)
- Associations between disease severity and PROs
- Associations between change in disease severity and change in PROs

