12.5 Risks, Insurance, Indemnity and compensation

This is a non-interventional observational study. It does not involve any direct patient intervention with respect to laboratory tests, examinations or drug treatment.

The Sponsor will provide Product Liability insurance for all subjects included in the study.

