### **3.5.2 Exposure/Independent Variables of Interest**

- **Patient demographics (if data available)**
  - Date of birth
  - Age at baseline
  - Age groups
  - Gender at birth
  - Marital status (married, unmarried)
  - Medical plan type
    - ✓ The type of healthcare plan each patient is enrolled in at baseline will be determined, including National/Public insurance, Private insurance, Employer benefits, and Other
- **Clinical characteristics**
  - Initial Diagnosis of Rheumatoid Arthritis (RA)
    - ✓ Year of initial diagnose
  - Initiation of Adalimumab
    - ✓ First time administration (DD/MM/YYYY)
    - ✓ Dosage of first injection (in mg)
  - Disease status of RA
    - ✓ Moderate (defined as Disease Activity Score in 28 Joints (DAS28) between 3.2 and 5.1)
    - ✓ Severe (DAS28>5.1)
  - Erythrocyte sedimentation rate (ESR) (in mm/hour)
  - C reactive protein (CRP) (in mg/L)
  - Disease Activity Score in 28 joints (DAS28)

To calculate the DAS28, the physician or specialist nurse will:

1. Count the number of swollen joints (out of the 28)

2. Count the number of tender joints (out of the 28)
3. Take blood to measure the erythrocyte sedimentation rate (ESR) or C reactive protein (CRP); the latest measurement in the medical records may also be used if a blood draw is not standard for that visit
4. Ask the patient to make a 'global assessment of health' which will be indicated by marking a 10 cm line between very good and very bad

The physician or specialist nurse will then mark each component score on the CRF and the DAS28 score if calculated (an online scoring calculator for the DAS28 can be found at <http://www.das-score.nl/das28/DAScalculators/dasculators.html>).

The DAS28 will be scored using the following formula:

$$\text{DAS28} = 0.56 * \text{sqrt}(\text{tender28}) + 0.28 * \text{sqrt}(\text{swollen28}) + 0.70 * \ln(\text{ESR or CRP}) + 0.014 * (\text{Global assessment of Health})$$

DAS28 scores will be interpreted using the following categorization:

- ✓ Remission:  $\text{DAS28} \leq 2.6$
  - ✓ Low Disease Activity:  $2.6 < \text{DAS28} \leq 3.2$
  - ✓ Moderate Disease Activity:  $3.2 < \text{DAS28} \leq 5.1$
  - ✓ High Disease Activity:  $\text{DAS28} > 5.1$
- comorbidities
- ✓ Myocardial infarction
  - ✓ Congestive heart failure
  - ✓ Peripheral vascular disease
  - ✓ Cerebrovascular disease
  - ✓ Dementia
  - ✓ Chronic pulmonary disease
  - ✓ Connective tissue disease
  - ✓ Ulcer disease
  - ✓ Mild liver disease
  - ✓ Diabetes

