- Additionally, in Excel Table 10.2, separate bivariate linear regression models will be estimated to identify the association between change in DAS28 and change in each of the PROs at 12 and 24 weeks after baseline respectively. If normality assumption for the residual of regression is violated, Spearman correlation coefficients and p-values will be estimated instead.
- In Excel Table 11, separate multivariate generalized linear models (GLM) will be estimated to test for the differential changes in primary and secondary efficacy outcomes after baseline, across the subgroups defined by the potential modifiers, including age, gender, baseline severity, and other diagnoses/comorbidities.

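### A week 12 or week 24 DAS28 may be built on an ESR or CRP taken before the first adalimumab dose, because the rule for using values on file sets no earliest date.

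*Protocol*

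**What the plan says.** Protocol 9.2.4.7 (Study Documents, clinical CRF) lists four DAS28 inputs: swollen joints, tender joints, ESR or CRP, and the patient's global assessment. The default for the third is to take blood, with an allowance: "the latest measurement in the medical records may also be used if a blood draw is not standard for that visit". SAP 3.5.2 repeats the allowance word for word. Neither document gives a maximum age for the value, limits the allowance to baseline, or requires that a follow-up value come from after treatment start.

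Table 1 in Protocol 9.1.1 schedules DAS28 at baseline, week 12, week 24 and early termination, so the allowance covers every follow-up score. A visit without a blood draw is foreseeable, because visits follow routine practice (Protocol 9.1) and Protocol 12.5 says of the study: "It does not involve any direct patient intervention with respect to laboratory tests, examinations or drug treatment".

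Change in disease severity to week 24 is a listed variable (Protocol 9.3). Protocol 9.7.6 plans "Associations between change in disease severity and change in PROs". SAP 5.5 implements this with regressions to "identify the association between change in DAS28 and change in each of the PROs at 12 and 24 weeks after baseline".

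On missing data, Protocol 9.7.10 allows developer-recommended imputation of PRO items and nothing else. SAP 3.5.5 says the same, apart from filling in a missing day in a date.

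**The concern.** If no blood was drawn between the first dose and the follow-up visit, the latest value on file is a pre-treatment one. Following the rule exactly then puts that value into an on-treatment score. If the baseline DAS28 used the same value, the marker term cancels from the change, and the recorded change reflects only joint counts and patient global. This is a baseline value carried forward for one component, in a plan that says it does not impute, and nothing in either document flags the affected scores.

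At stake are the size of the DAS28 change and the analyses that relate it to change in HAQ DI, SF-36, EQ-5D-3L and WPAI. About 52 patients are planned (Protocol 9.5), so a modest number of affected scores could matter.

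**Working it through.** The plan states no figure on this point, so there is none to reproduce. The size follows from its own DAS28 formulas.

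**Inputs from the documents**
- Marker term in DAS28(ESR), Protocol 9.2.4.7: 0.70 × ln(ESR).
- Marker term in DAS28(CRP), Protocol 9.2.4.7: 0.36 × ln(CRP + 1).
- Marker term in SAP 3.5.2, for either marker: 0.70 × ln(ESR or CRP).

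**Assumed, because the documents do not give them:** the fall in the marker on treatment, and the share of follow-up scores that use a pre-treatment value.

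**Step 1. Loss per affected score.** With the baseline value reused, the change loses 0.70 × ln(ESR0/ESR1), or 0.36 × ln[(CRP0 + 1)/(CRP1 + 1)].

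| True course of the marker | Calculation | DAS28 change lost |
|---|---|---|
| ESR to 70% of baseline | 0.70 × ln(1/0.70) | 0.25 |
| ESR 40 to 20 | 0.70 × ln(2) | 0.49 |
| ESR 40 to 10 | 0.70 × ln(4) | 0.97 |
| CRP 20 to 5 mg/L, protocol formula | 0.36 × ln(21/6) | 0.45 |
| CRP 20 to 5 mg/L, SAP formula | 0.70 × ln(4) | 0.97 |

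The last two rows differ because the protocol and SAP formulas for CRP differ. Those formulas need reconciling in any case.

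**Step 2. One whole score.** Assumed patient: tender joints 10 to 3, swollen joints 8 to 2, patient global 60 to 30 mm, ESR 40 to 20.
- Baseline: 0.56√10 + 0.28√8 + 0.70 ln 40 + 0.014 × 60 = 5.99.
- Follow-up with the current ESR: 0.56√3 + 0.28√2 + 0.70 ln 20 + 0.014 × 30 = 3.88, a change of −2.10.
- Follow-up with ESR 40 carried: 4.37, a change of −1.62.

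About 77% of the change is kept (1.62/2.10). With CRP 20 to 5 and the protocol formula, the change is −2.07, or −1.62 if CRP is carried (78% kept).

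**Step 3. Group mean.** If a share p of scores is affected and ESR halves, the mean change is understated by p × 0.485. That is 0.05 at p = 10%, 0.12 at 25%, 0.24 at 50% and 0.49 at 100%. With ESR falling to between 70% and 30% of baseline, the range is 0.03 to 0.08 at p = 10% and 0.25 to 0.84 at p = 100%.

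**Step 4. Association with PRO change.** Write DAS28 change as C + M, where C is the joint-count and global part and M the marker part. Assume SD(C) = 0.9; M with mean −0.485 and SD 0.5; corr(C, M) = 0.2; PRO change with SD 1 and correlation 0.5 with C. Let r be the correlation of M with PRO change. Half the scores, at random, lose M.
- Variance of DAS28 change without carrying: 0.81 + 2 × 0.09 + 0.25 = 1.24.
- Variance with half carried: 0.81 + 0.09 + [0.5 × (0.25 + 0.485²) − (0.5 × 0.485)²] = 1.08.
- If r = 0, the covariance with PRO change is 0.45 either way, and the correlation rises from 0.45/√1.24 = 0.40 to 0.45/√1.08 = 0.43.
- If r = 0.6, the covariance is 0.75 without carrying and 0.60 with it, and the correlation falls from 0.67 to 0.58.

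The direction turns on correlations that the documents do not give.

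**The case against.** The strongest case against is that the reach is narrow. The allowance applies only where a draw is not standard at that visit, and it touches one component of four. The analysis it feeds is additional secondary in the protocol and exploratory in the SAP. All of that stands and limits the weight of the point. It does not make a pre-treatment marker a valid part of an on-treatment score.

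A reader might infer more than the documents support:

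- **That the rule contradicts the visit window.** Protocol 9.1 says "Data at the clinic visits within ± 7 days of the study-defined time points will be collected". That governs clinic visits, not the date of a value taken from the records. The window leaves the gap open; it does not conflict with the rule.
- **That the associations with PRO change must be weakened.** Step 4 shows that they can move either way. If every patient's change shrank by the same proportion, the correlation would not move at all. SAP 5.5 also does not say which variable is the predictor, and it may switch to Spearman.
- **That reported follow-up disease categories will be wrong.** SAP 5.2 categorises DAS28 at baseline only, and no table listed in SAP section 6 reports follow-up categories.
- **That the error always hides improvement.** It does so only if the marker falls on treatment. If the marker rises, a carried value overstates improvement.

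It is also fair to object that a ±7-day limit on the sample date would discard genuine on-treatment values, for example one taken 10 days before the visit. SAP 3.5.5 itself doubts that missing data here are missing at random. That argues for a lighter fix, which is the one given below.

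**Conclusion.** The point holds, as a limited correction that should be made. As written, the rule allows a week 12 or week 24 DAS28 to carry a pre-treatment ESR or CRP, against the plan's own statement that it does not impute. Where that happens and the marker falls, the patient's DAS28 change is understated, by 0.49 if ESR halves and by 0.45 if CRP goes from 20 to 5 mg/L under the protocol formula. These sizes rest on assumed laboratory values. The frequency is unknown, so the effect on the group mean can only be given as a range.

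The association between DAS28 change and PRO change is distorted in a direction that cannot be settled from the documents. A reader might also infer that the main result is at risk. It is not: the primary and main secondary tests are paired comparisons of HAQ DI and contain no follow-up DAS28. The sensitivity ANCOVA adjusts for baseline severity, not follow-up severity.

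**What to change.** State in Protocol 9.2.4.7 and SAP 3.5.2 that a DAS28 after baseline may use only an ESR or CRP sampled after the first adalimumab dose, and that otherwise DAS28 is missing for that visit. Use the sample date where it is available, and report by visit how many values were excluded for this reason. SAP 3.5.5 assigns day 15 when the day is missing, so say how a sample dated only to the month of the first dose is treated. A tighter look-back, such as ±7 days around the visit, can be a sensitivity analysis.

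No extra blood draw is needed. The cost is that some follow-up DAS28 values become missing. How many is unknown, since the same frequency drives both the error and the loss. This fits the available-data approach in Protocol 9.7.10 and SAP 3.5.5.

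Timing is a further limit. Data collection was planned to end on 30 June 2018 (Protocol 6.0), and the latest SAP version is dated 30 May 2019. The CRF is a separate document, so it is not known whether sample dates were recorded. The rule can be applied to data already collected only where they were. For the remaining scores, the study report should say that the marker's date could not be verified.

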The WPAI is a patient-reported questionnaire to measure work and activity impairment during the past seven days. It determines employment status, hours missed from work due to the disease (i.e. RA), hours missed from work for other reasons, hours actually worked, the degree to which the disease affected work productivity while at work and the degree to which the disease affected activities outside of work. Additional questions around employment status will be incorporated into the survey. The completion time for the WPAI is approximately 2-5 minutes. The full version of WPAI is presented in **Error! Reference source not found.**

All of the above questionnaires will be used with the validated Chinese version.

Patient Global Impression of Change (PGIC)

The PGIC measures the patient's perceptions of changes in their disease. It consists of one question asking about the change in their condition; for this study, the base will be "since you initiated your adalimumab treatment". The completion time for the PGIC is less than 1 minute. The full version of PGIC is presented in **Error! Reference source not found.**

Patient Treatment Satisfaction Questions

The patient treatment satisfaction questions were developed de novo for this study and are not considered "validated" questions. Self-administered by the patient, the completion time for the patient treatment satisfaction questions is approximately 1-2 minutes. The full version of patient treatment satisfaction questions are presented in **Error! Reference source not found.**

Healthcare Resource Utilization (HCRU) Questionnaire

The HCRU questionnaire will collect data on the healthcare resources consumed in the prior 3 months, as recall beyond 3 months may be problematic in an older population (16). HCRU collection will include data such as the number of physician visits and to which physician (GP, specialist), Emergency Department visits, hospitalizations, and other drugs as well as devices and aids purchased to assist in their mobility due to RA. The HCRU questionnaire will be part of the patient questionnaire and will be distributed to patients together with the PRO questionnaires (Appendix D to Appendix I). The full HCRU questionnaire is presented in **Error! Reference source not found.J** and will be used with the validated Chinese version.

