9.3 Variables

Variables:

Primary Variable

- Change in HAQ DI score at week 24 from the baseline

Secondary Variable

- Change in HAQ DI score at week 12 from the baseline
- Change in other PROs (SF-36 domain scales, EQ-5D Index, Work Productivity and Activity Impairment Questionnaire [WPAI]) from baseline to weeks 12 and 24
- Number and percent of patients achieving a clinically meaningful improvement on the HAQ DI, from baseline to weeks 12 and 24

Additional Secondary Variable

- Change in HAQ DI score from baseline to week 24
- Changes in the disease severity and PROs from baseline to week 24
- Healthcare Resource Utilization (HCRU) at baseline, weeks 12 and 24

Exploratory Variable

- Change in patient satisfaction questions from baseline to weeks 12 and 24
- Patient's impression of change at weeks 12 and 24 from baseline

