#### **Additional Inclusion Criteria**

- Female subjects who are either not of childbearing potential, defined as postmenopausal for at least 1 year or surgically sterile (bilateral tubal ligation, bilateral oophorectomy and/or hysterectomy) or are of childbearing potential and are practicing an approved method of birth control throughout the study and for 150 days after the Week 24 dosing or the last dose of adalimumab.

- Subjects judged to be in good health as determined by the Principal Investigator based upon the results of medical history, laboratory profile, physical examination, chest x-ray (CXR), and a 12-lead electrocardiogram (ECG) performed no more than 3 months (90 days) have passed.
- Subjects have negative TB Screening records. If a subject has evidence of a latent TB infection, the subject must initiate and complete a minimum of 1 month (per China guideline) of an ongoing TB prophylaxis or have documented completion of a full course of TB prophylaxis, prior to Baseline

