### **3.5 Definitions of Study Variables**

The key variables of interest in this study are demographic and clinical characteristics, patient-reported health and disability outcomes, and healthcare resource utilizations. Most variables will be measured at baseline (i.e. index), and at weeks 12 and 24 after

the initiation of Adalimumab; healthcare resource utilization will be summarized over the 6 month post-index period.

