## 5.5 Analysis Plan for Exploratory Objectives

- Excel Table 7 describes the change in 4 patient satisfaction questions at weeks 12 and 24 after the initiation of adalimumab, in those patients continuing on adalimumab (observed population). These changes will be summarized as number and percentage of each response and compared with Wilcoxon signed rank test. Satisfaction will also be dichotomized and analyzed over time with Cochran-Armitage test for trends.
- Excel Table 8 summarizes the patients' global impression of change in RA at weeks 12 and 24 after the initiation of adalimumab, in those patients continuing on adalimumab (as observed population). Each response (very much better, much better, a little better, no change, a little worse, much worse, and very much worse) will be summarized as number and percentage.
- Descriptive statistics will be presented for post-index overall RA related direct healthcare resource utilization (Excel Table 9)
  - Consultations/visits to healthcare professionals for treatment of RA (number of patients with  $\geq 1$  visit; categorized by the treatment department listed in 3.5.4)
  - Procedures received when visiting the healthcare professional(s) for treatment of RA (number of patients with  $\geq 1$  procedure; categories listed in 3.5.4)
  - surgeries received when visiting the healthcare professional(s) for treatment of RA (number of patients with  $\geq 1$  surgery; categories listed in 3.5.4)
  - Hospitalizations in relation to RA (number of patients with  $\geq 1$  admission)
  - Length of stay in days (mean, SD, median)
  - Concomitant medications taken for RA (number of patients with  $\geq 1$  medication; categories listed in 3.5.4))

- Associations between disease severity (measured by DAS28) and PROs (HAQ DI score, SF-36 domain scales, EQ-5D-3L index, WPAI outcomes) will be analyzed using the bivariate linear regression model (Excel Table 10.1). Separate models will be estimated to identify the association between DAS28 and each of the PROs. If normality assumption for the residual of regression is violated, Spearman correlation coefficients and p-values will be estimated instead.

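### The fixed 3-month recall on follow-up HCRU forms can carry resource use from before adalimumab into a summary labelled post-index

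*Protocol*

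**What the plan says.** - **Recall.** Protocol 9.2.4.7: "The HCRU questionnaire will collect data on the healthcare resources consumed in the prior 3 months". The only reason given is that longer recall may be unreliable. No visit has its own wording.
- **Schedule.** Protocol 9.3 lists "Healthcare Resource Utilization (HCRU) at baseline, weeks 12 and 24". Table 1 in 9.1.1 also marks the HCRU row in the column "Early Termination / Drop out". A footnote to that table says that a 7-day "window is permitted around scheduled study visits".
- **Follow-up.** Protocol 9.1: "The observation period for each patient is 24 weeks". Inclusion criterion 4 places the start of adalimumab at the baseline visit, so baseline is the index date.
- **Reporting.** SAP 3.5: "healthcare resource utilization will be summarized over the 6 month post-index period". SAP 5.5 describes Excel Table 9 as post-index and RA-related. It gives the number of patients with at least one visit, procedure, surgery, admission or medication, and the mean, SD and median of length of stay.
- **What is absent.** SAP 3.5.5 (conventions) has no rule that removes use dated before adalimumab or use reported on two forms, and none that says whether early-termination forms enter Table 9. The questionnaire is not part of the two documents, so its item wording cannot be checked.

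**The concern.** Three calendar months is longer than the 12 weeks between scheduled visits, and much longer than the time on treatment of a patient who stops early. A follow-up form completed as described therefore asks partly about the period before the first dose, yet its answers go into a table labelled post-index. Most of Table 9 counts patients with at least one event, so one pre-treatment event is enough to classify a patient as a post-index user. The study is meant to inform payers, and resource use is one of its stated aims. An anchored question was also within reach: in the same protocol section, the PGIC asks about change since adalimumab was started.

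**Working it through.** **Inputs.** Recall R = 3 months = 365.25/12 × 3 = 91.3 days, taken as 91 (calendar range 89 to 92). Week 12 = day 84, with window days 77 to 91. Week 24 = day 168, with window days 161 to 175. Dropout is 10% of 52 patients (Protocol 9.5), or 13% with a range of 10 to 15% (SAP 4) applied to 55 patients (SAP 3.1).

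**The plan's own figure.** The recall is a definition, so there is nothing to reproduce. The only computed figure used here is N = 52. A paired t-test with mean change −0.21, SD 0.5, two-sided 0.05 and 80% power needs 47 evaluable patients; 47 × 1.1 = 51.7 gives 52, and 47/0.9 = 52.2 gives 53. The planned N is reproduced to within one patient.

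**1. Week 12 form.** Pre-index days = max(0, R − visit day).
- Day 84: 91 − 84 = 7 days, 7/91 = 7.7% of the recall
- Day 77: 91 − 77 = 14 days (15.4%)
- Day 91: 0 days
- With R from 89 to 92, the day-84 figure is 5 to 8 days.

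**2. Early-termination form at week w.** Pre-index share = (91 − 7w)/91.

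| Week | Pre-index days | Share |
|---|---|---|
| 4 | 63 | 69% |
| 6 | 49 | 54% |
| 8 | 35 | 38% |
| 10 | 21 | 23% |
| 13 | 0 | 0% |

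After Week 13 nothing is pre-index, but the form overlaps the Week 12 form (at Week 16: 91 − 28 = 63 days).

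**3. Week 12 and Week 24 recalls.** Overlap = max(0, R − gap).
- On schedule: 91 − 84 = 7 days
- Shortest gap (days 91 to 161): 91 − 70 = 21 days
- Longest gap (days 77 to 175): none; 98 − 91 = 7 days fall in neither recall

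Two scheduled recalls total 2 × 91 = 182 days against 168 observed. The excess of 14 days is 7 pre-index plus 7 covered twice. An event reported twice still makes one patient with at least one event, so among the Table 9 outputs only length of stay can be double counted.

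**4. Patients concerned.** 52 × 0.10 = 5.2; 55 × 0.13 = 7.2 (at 15%, 8.3). Only those who stop before about Week 13 and complete a form add pre-index time. Protocol 12.6 gives no early-termination form to patients who cannot be contacted.

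**5. Illustration under an assumed constant event rate, equal before and after index.** Entries are the probability of at least one event. The documents give no rate, so a range is shown.

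| Rate per month | 168 days | Both recalls, on schedule (175.3 days) | True 28 days to Week 4 | Week 4 form (91.3 days) |
|---|---|---|---|---|
| 0.05 | 24.1% | 25.0% | 4.5% | 13.9% |
| 0.25 | 74.8% | 76.3% | 20.5% | 52.8% |
| 1 | 99.6% | 99.7% | 60.1% | 95.0% |

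For patients who complete the visits the effect is about 1.5 percentage points or less. For a Week 4 stopper the form overstates use on treatment, but still gives less than a full 24 weeks would.

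**The case against.** **Early-termination forms may never reach Table 9.** Protocol 9.3 and SAP 3.1 name only baseline, Week 12 and Week 24. This stands: their inclusion is an inference. There is evidence for it. Unlike the text for Tables 7 and 8, the text for Table 9 is not limited to patients continuing adalimumab, and the bar in SAP 3.5.5 on assessment after discontinuation concerns efficacy measures. The SAP needs to settle the question.

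**Three months may just mean 12 weeks.** The protocol uses 6 months and 24 weeks interchangeably, and patients do not recall to the week. On that reading the scheduled forms tile the follow-up when visits are on time. But a day-77 visit would still reach 84 − 77 = 7 days back, and a Week 4 early-termination form would still be (84 − 28)/84 = 67% pre-index.

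**Entry tests.** A reader might infer that the eligibility work-up will be counted as post-index procedures, because SAP 3.5.4 lists chest X-ray, electrocardiogram, blood sample and tuberculin test. The documents do not support this as a general result. The SAP's additional inclusion criteria accept examinations up to 90 days old, so many may fall outside a 7-day leak, and SAP 3.5.4 counts procedures for treatment of RA, which screening is not clearly part of. It remains a possibility, mainly on early forms.

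**Comparability.** Anchoring makes the follow-up recall differ from the baseline recall. This is true, but at scheduled visits the difference is about a week.

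**Conclusion.** The point holds as a labelling and window defect of modest size. If the plan is followed as written, the Week 12 form can place about 7 days of pre-adalimumab use (0 to 14 within the window) in a post-index table. Early-termination forms before about Week 13 can place far more there, but only if the SAP means to include them, and for at most about 5 to 7 patients at the planned 10 to 13% dropout. This assumes that patients take 3 months literally, that forms are completed on the visit day, and that baseline is the first dose.

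Three stronger readings go beyond the documents:
- **Resource use and costs are overstated.** The net direction is unknown, because early stoppers also contribute less follow-up to a 6-month summary. Costs are mentioned in Protocol 9.1 and SAP 3.1, but no cost table appears in SAP 5.5 or 6.
- **Many patients are affected.** SAP 1.1 cites average use of only 3 months in China, but neither document gives a distribution of stopping times, and patients judged unlikely to adhere for 24 weeks are excluded.
- **Fourteen days (14/168 = 8%) of pre-index use.** Half of these days are overlap between the two follow-up recalls, which leaves the patient counts unchanged.

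HCRU is an additional secondary outcome in the protocol and exploratory in the SAP, and it is descriptive in both. The HAQ DI analysis is not affected.

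**What to change.** 1. **Questionnaire.** At Week 12, Week 24 and early termination, ask about use since the later of the baseline visit and the last completed HCRU form, capped at 3 months. Keep the 3-month recall at baseline.
2. **SAP 3.5 and 5.5.** Define the post-index window as starting at adalimumab initiation, and reconcile the 6-month period with the 24 weeks of observation. State whether early-termination forms enter Table 9; exclude those whose recall extends before baseline, or show them separately.
3. **If data were collected with the 3-month wording.** This is likely: the protocol milestones plan the end of data collection for 30 June 2018, and the latest SAP version is dated 30 May 2019. Apply item 2, add a sensitivity version of Table 9 without early-termination forms, and report the Week 12 leak of about one week and the possible double counting of length of stay as limitations.

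Reporting use per patient-month covered is an optional extra.

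**Cost.** A minor adaptation of the validated Chinese wording, a follow-up recall slightly different in length from baseline, a few lines in the SAP and one additional table.
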